15. GOOD CLINICAL PRACTICE

14.1. Declaration of Helsinki

The Investigator will ensure that this clinical investigation is conducted in full conformity with the current revision of the Declaration of Helsinki (last amended October 2000, with additional footnotes added 2002 and 2004).

14.2. Guidelines for GCP

The Investigator will ensure that this clinical investigation is conducted in full conformity with relevant regulations and with the International standard for Good Clinical Practice for clinical investigations of medical devices for human subjects (ISO 14155:2011).

14.3. Ethics review

The clinical investigation plan, Investigator's Brochure, Case Report Forms (CRFs), informed consent form, participant information sheet and any other documents needed for review by an appropriate Ethics Committee (EC) or regulatory authority will be submitted to obtain written approval. Any additional requirements imposed by the EC or regulatory authority will be followed, if appropriate. The trial will be conducted in compliance of the Belgian Law of 7 May 2004 on experiments on the human person.

The Investigator will submit and, where necessary, obtain approval for all amendments to the original approved documents. Furthermore, the clinical investigation will not begin until the required approval/favorable opinion of the EC or regulatory authority has been obtained.

14.4. Patient Information and Consent Form

The Principal Investigator will ensure that the subject is given full and adequate oral and written information about the nature, purpose, possible risks and benefits of the investigation. Subjects must also be notified that they are free to discontinue participation in the investigation at any time. The subject should be given the opportunity to ask questions and time for consideration.

The subject's signed informed consent has to be obtained before collecting any investigation related procedures. The original must be filed by the Principal Investigator. A copy of the Patient Information including the signed Consent Form should be given to the subject. If modifications are made according to local requirements, the new version must be approved by the EC.

14.5. Subject data protection

The clinical investigation staff will ensure that the participants' anonymity is maintained. The participants will be identified only by a sequential ID number on the eCRF. All documents will be stored securely and only accessible by clinical investigation staff and authorized personnel. The clinical investigation will comply with the Data Protection Act which requires data to be pseudonymized as soon as it is practical to do so.

14.6. Procedures in case of medical emergency

The Principal Investigator is responsible for ensuring that procedures and expertise are available to cope with medical emergencies during the investigation.

16. CLINICAL INVESTIGATION CONDUCT RESPONSIBILITITES

15.1. Clinical investigation plan amendments

Amendments to the clinical investigation plan must be submitted to the Sponsor for review before submitting to the appropriate EC and Regulatory Authority for approval.

15.2. Clinical investigation plan violations, deviations and serious breaches

The Clinical investigator will not implement any deviation from the clinical investigation plan without agreement from the Sponsor, except where necessary to eliminate an immediate hazard to clinical investigation participants.

In the event that the Clinical investigator needs to deviate from the clinical investigation plan, the nature of and reasons for the deviation will be recorded in the CRF and notified to the Sponsor. If this necessitates a subsequent clinical investigation plan amendment, this will be submitted to the Sponsor for approval and then to the appropriate REC and Regulatory Authority for review and approvals as appropriate. It is Sponsor policy that waivers to the clinical investigation plan will not be approved.

In the event that a serious breach of GCP is suspected, this will be reported to the Sponsor immediately.

15.3. End of clinical investigation

The end of clinical investigation is defined as the last participant's last visit.

The investigator and/or the clinical investigation steering committee have the right at any time to terminate the clinical investigation for clinical or administrative reasons.

The end of the clinical investigation will be reported to the EC and Regulatory Authority within 90 days, or 15 days if the clinical investigation is terminated prematurely. The Investigators will inform participants of the premature clinical investigation closure and ensure that the appropriate follow up is arranged for all participants involved.

A summary report of the clinical investigation will be provided to the EC and Regulatory Authority within 1 year of the end of the clinical investigation.

15.4. Insurance and indemnity

In accordance with the Belgian Law relating to experiments on human persons dated May 7, 2004, Sponsor shall assume, even without fault, the responsibility of any damages incurred by a Study Patient and linked directly or indirectly to the participation to the Study, and shall provide compensation therefore through its insurance."

15.5. Funding

This is a monocentric, academic field observation study. A study grant will also be provided by DORC BV to cover the administrative and personnel expenses for this study.

17. REPORTING, PUBLICATIONS AND NOTIFICATIONS OF RESULTS

16.1. Authorship policy

Ownership of the data arising from this clinical investigation resides with the clinical investigation team. On completion of the clinical investigation, the clinical investigation data will be analyzed and tabulated, and a clinical investigation report will be prepared in accordance with ISO14155:2011.

16.2. Publication

The Principal Investigator intents to publish the obtained study data in a specialized journal for retinal surgery. The statistician will provide a study report, which will be used as source data to write the results section of the manuscript. The publication will also cover authorship, acknowledgements (mentioning the grant provider of the trial), and an overview of relevant scientific publications.

Before submitting for publication, the manuscript will be sent to the grant provider, allowing the grant provider give feedback on the manuscript within 2 weeks. It is up to the Principal Investigator to decide to make any changes to the manuscript based on this feedback.

18. SAFETY REPORTING

18.1 Definitions

The definitions and reporting requirements adopted in this Clinical Investigation Plan (CIP) are based on the ISO 14155:2011 standard and the MEDDEV 2.7/3 – rev 3 guideline.

18.1.1. Adverse Event (AE)

An AE is any untoward medical occurrence, unintended disease or injury or any untoward clinical signs (including an abnormal laboratory finding) in subjects, users or other persons whether or not related to the investigational medical device.

Note 1: This definition includes events related to the investigational medical device or the comparator.

Note 2: This definition includes events related to the procedures involved.

Note 3: For users or other persons, this definition is restricted to events related to investigational medical devices.

18.1.2. Serious Adverse Event (SAE)

A SAE is an adverse event that:

- a) led to death,
- b) led to serious deterioration in health of the subject, that either resulted in:
 - a life-threatening illness or injury, or
 - a permanent impairment of a body structure or a body function, or
 - requires in-patient hospitalization or prolongation of existing hospitalization, or
 - in medical or surgical intervention to prevent life threatening illness or injury or permanent impairment to a body structure or a body function,
- c) led to fetal distress, fetal death or a congenital abnormality or birth defect.

Note: Planned hospitalization for pre-existing condition, or a procedure required by the CIP, without a serious deterioration in health, is not considered a serious adverse event.

18.1.3. Adverse Device Effect (ADE)

An ADE is an adverse event related to the use of an investigational medical device.

Note 1: This includes any adverse event resulting from insufficiencies or inadequacies in the instructions for use, the deployment, the implantation, the installation, the operation, or any malfunction of the investigational medical device.

Note 2: This includes any event that is a result of a use error or intentional misuse of the investigational medical device.

18.1.4. Serious Adverse Device Effect (SADE)

A SADE is an adverse device effect that has resulted in any of the consequences characteristic of a serious adverse event.

18.1.5. Unanticipated Serious Adverse Device Effect (USADE)

An USADE is a serious adverse device effect which by its nature, incidence, severity or outcome has not been identified in the current version of the risk analysis report.

Note: An anticipated serious adverse device effect (ASADE) is an effect which by its nature, incidence, severity or outcome has been identified in the risk analysis report.

18.1.6. Device Deficiency (DD)

A DD is an inadequacy of an investigational medical device with respect to its identity, quality, durability, reliability, safety or performance.

Note: This may include malfunctions, use errors, and inadequate labelling.

18.2 Adverse Events that do not require reporting

In general, the following should not be reported as AEs:

- Pre-existing conditions, including those found as a result of screening (these should be reported as medical history or concomitant illness).
- Pre-planned procedures, unless the condition for which the procedure was planned has worsened from the first trial-related activity after the subject has signed the informed consent.

The following events are commonly observed and are therefore not considered as adverse events for the purpose of the trial:

- Decreased visual acuity compared to preoperative measurement
- Reddish eye
- Moderately and temporarily increased ocular pressure (<35 mmHg)
- Mild to moderate intra-ocular inflammation
- Mild corneal edema

All these events will be recorded in the patient's medical notes according to routine practice.

The following events not to be considered as SAEs are:

- Pre-planned hospitalizations unless the condition for which the hospitalization was planned has worsened from the first trial-related activity after the subject has signed the informed consent.
- Hospitalization as part of a standard procedure for protocol therapy administration. However, hospitalization or prolonged hospitalization for a complication of therapy administration will be reported as an SAE.
- Hospitalization or prolongation of hospitalization for technical, practical, or social reasons, in absence of an AE.

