A powerful light source is required to illuminate the inside of the globe during surgery. For this purpose, a PMMA fiber is connected to the light source of the vitrectomy machine and guided into the eye.

Historically, a halogen light source was used. About 15 years ago, more powerful Xenon light sources became available and are still present in many vitrectomy devices. More recently, LED light sources became more popular. Also our present vitrectomy device (DORC EVA) is equipped with an LED light source.

Increasing light output is required when using ultra-small gauge surgery (27G), since the diameter of the light fiber is extremely thin. However, care must be taken by the surgeon to avoid light toxicity when the light source is held too close to the same area of the retina for too long. Retinal damage due to light toxicity after vitrectomy can have a major effect on the visual acuity of the patient.

In most light sources for vitrectomy surgery, the light is filtered, eliminating more bluish wavelengths to increase its safety.

5. Phaco ultrasound.

To remove an opacified lens from the eye (cataract), the lens needs to be emulsified in the eye. For this purpose, a small needle is used that is oscillating on an ultrasonic frequency. These oscillations emulsify the lens material, after which can be aspirated (using the aspiration system of the device). The DORC EVA has an analog driver board and operates at a frequency of 40 kHz.

6. Laser module.

To reattach the retina in case of retinal detachment, laser coagulates need to be placed around the breaks in the retina. For this purpose, a vitrectomy machine has a built-in laser module. A glass fiber is used to guide the laser light into the eye on the retina. Using the foot switch of the device, laser coagulates can be directed towards the desired location on the retina. The DORC EVA uses a 532 nm endo laser which has been the standard for ophthalmic use.

7. Silicone oil injection.

Not infrequently, the eye needs to be filled with silicone oil during surgery for retinal detachment. For this purpose, a system is present that drives the silicone oil from a (glass) syringe into the eye. The DORC EVA can drive (pre) filled syringes of silicon oil with a pressure up to 6 bars.

8. Silicone oil extraction.

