5.3 Patient safety with the EVA Nexus device

This field observation study will be performed to obtain more information on the safety and daily use of the EVA Nexus device in routine phaco/vitrectomy surgery. This information can lead to small adjustments to the device to further fine tune a safe device which can be used by other surgeons.

During a vitrectomy surgery, the surgeon removes the vitreous gel. This is done using a mini-guillotine of half millimeter diameter (or even less in 27G surgery) that is inserted in the eye. Meanwhile, an infusion fluid is injected in the eye. Sufficient fluid irrigation is mandatory to avoid a drop in the eye pressure which can lead to retinal or choroidal hemorrhage. On the other hand, it must be avoided to have the eye pressure elevate too high, since this can block the arterial blood supply which can lead to permanent damage of the eyesight of the patient.

The EVA Nexus device has an automated system, which allows better control of the eye pressure during the surgery compared to existing vitrectomy technology.

Another novel feature on this device is the improvement of the guillotine itself. The faster the guillotine can go backwards and forwards, the safer the surgery can be performed. The EVA Nexus device can keep up to a speed of 20000 cuts per minute, whereas in even the most performant devices the speed is limited to 16000 cuts per minute.

Often vitrectomy is combined with lens surgery. The removal of the lens is nowadays done using a device that emulsifies the lens with ultrasonic waves. This technique is called "phaco-emulsification", which has been the golden standard in cataract surgery for more than 20 years. The hand-held phaco-emulsification probe connected to the EVA Nexus is the same probe as used on our present DORC EVA device, but the internal steering is redesigned to allow better fine-tuning of the surgical settings according to the preferences of the surgeon.

Besides the EVA Nexus itself, several of the disposable supplies of this surgical platform were optimized:

- Newly designed phaco needles improve anterior chamber stability during cataract surgery.
- The instrument cannulas used during vitrectomy were redesigned. The smaller outside part occupies less space hence will allow more movement of the eye during the surgery.

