7.2 Study Flowchart

	Preop (inclusion)	Surgery	Postop day 1
Vitrectomy		X	
Visual acuity	X		X
Eye pressure	X		X
Biomicroscopy	X		X
Ophthalmoscopy	X		X
OCT	X ¹		
Ultrasound	X ²		X ²
Adverse events	X ³		X
Surgical summary		X	

X¹ if required, depending on indication for surgery, e.g.: macular pucker, macular hole, vitreomacular traction, ...

X² if required, depending on indication for surgery, e.g.: vitreous hemorrhage

X³ any pre-operative clinical condition that is known to affect the incidence of (S)AE's during surgery (e.g. zonular dehiscence, tamsulosine medication, axial length, ...)

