11.4.1 Adverse events that do not require reporting

After vitrectomy, the following transient adverse events are commonly present during the first day after surgery, hence will not require reporting:

- Decreased visual acuity compared to preoperative measurement
- Reddish eye
- Moderately and temporarily increased ocular pressure (<35 mmHg)
- Mild to moderate intra-ocular inflammation
- Mild corneal edema In addition see section 18.2.

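### Section 18.2 exempts any loss of visual acuity from adverse-event status without a limit, so vision loss with no diagnosis by day 1 may go uncounted in the secondary safety objective

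*Combined protocol and SAP*

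**What the plan says.** Section 18.2 states: "The following events are commonly observed and are therefore not considered as adverse events for the purpose of the trial". The first item under that sentence is "Decreased visual acuity compared to preoperative measurement". Four more follow: a red eye, a moderate and temporary pressure rise below 35 mmHg, mild to moderate inflammation, and mild corneal oedema. All five are to be written in the patient's "medical notes according to routine practice".

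Section 11.4.1 carries the same five items under a different introduction: "the following transient adverse events are commonly present during the first day after surgery, hence will not require reporting". It then points to Section 18.2.

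The background sections name loss of vision as the consequence of hazards of this surgery. Section 5.1, on light sources: "Retinal damage due to light toxicity after vitrectomy can have a major effect on the visual acuity of the patient". Section 5.3, on eye pressure that rises too high: "this can block the arterial blood supply which can lead to permanent damage of the eyesight of the patient". Section 5.2 adds that excessive infusion flow can cause ischaemic damage.

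The flowchart in Section 7.2 has a row for "Visual acuity", marked before surgery and on postoperative day 1. Section 5.3 ends data acquisition at the day-1 visit. Section 6 makes detection of day-1 (S)AEs related to the platform a secondary objective.

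**The concern.** A drop in vision on the day after intra-ocular surgery is common and usually uninformative, so exempting routine loss is reasonable. The difficulty is that Section 18.2 does not stop at routine loss. Read as written, it covers any fall from the pre-operative measurement, however large and whatever its origin.

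The protocol itself links light exposure and raised pressure to lasting visual harm, and it presents automated pressure control as a main feature of the new device. Vision is a direct functional sign that something has gone wrong on either account. The day-1 visit is the only postoperative look the study takes. If an unexplained severe loss at that visit is by definition not an adverse event, the secondary safety objective can miss it, and the safety report would give no hint of the omission.

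**Working it through.** The plan states no figure on this point, so the check sets the rules side by side.

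1. **Is the acuity item limited?** Section 18.2 limits pressure by degree, duration and a number (below 35 mmHg), inflammation to mild or moderate, and corneal oedema to mild. The acuity item has no limit of any kind. The red-eye item has none either.

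2. **Do the two lists agree?** Section 11.4.1 treats the items as adverse events that are transient and need no reporting. Section 18.2 says they are not adverse events and omits the condition of transience. These are different statuses with different conditions.

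3. **Can transience be checked?** Section 5.3 ends data acquisition at day 1. Section 18.3.2 closes reporting at the last follow-up visit if that comes before 7 days after last use of the device, and here it does. Whether a day-1 loss later recovers lies outside the study data.

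4. **Does the general recording rule catch it?** Section 18.3 has two limbs. A diagnosis, where there is one, is reported in place of its signs. Without a diagnosis, each sign is recorded as its own adverse event. The first limb still works for acuity loss with a known cause. The second is cancelled for acuity by the specific exemption in Section 18.2. The gap is therefore loss with no diagnosis by day 1.

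5. **Does seriousness catch it?** Section 18.1.2 defines an SAE as a kind of adverse event. Something that Section 18.2 says is not an adverse event has no clear route to the permanent-impairment criterion. The provision in Section 18.3.3 for SAEs found after the trial has the same dependence unless a diagnosis is made later.

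6. **Would the cause be found by day 1?** Often, but not always. Section 7.2 schedules biomicroscopy and ophthalmoscopy on day 1, and ultrasound where indicated, but no postoperative OCT. Appendix A names haemorrhages, retinal tears and surgically caused retinal or optic-nerve damage. It names neither light toxicity nor ischaemia, though it has a free-text field for other complications.

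7. **Is acuity analysed in another way?** Sections 13.1 and 14.5 name no analysis of acuity change. Section 14.5 promises summary statistics for the whole group without saying for which variables.

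**Scale, as illustration only.** The documents give no rate for vision loss without a diagnosed cause. Assume a rate p among 250 patients. The expected number is 250p, and the chance of at least one case is 1 − (1 − p)^250.

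| Assumed p | Expected cases | Chance of at least one |
|---|---|---|
| 0.5% | 1.25 | 71% |
| 1% | 2.5 | 92% |
| 2% | 5 | 99% |

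If every such case were exempt, the recorded count would be 0 of 250. The exact two-sided 95% upper limit would be 1 − 0.025^(1/250) = 1.5%. That limit would not be informative, because the zero would come from the recording rule and not from observation.

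**The case against.** The strongest reply is that Section 18.2 exempts a sign, not its cause. Section 18.3 asks for the diagnosis, Appendix A covers most surgical causes of vision loss, and the day-1 examination is there to look for such events. Section 11.4.1 cross-refers to Section 18.2 and both speak of common findings, so a sensible investigator would read them together and would not ignore a profound loss. Stopping at day 1 is a reasoned choice set out in Section 5.3. This stands, and it confines the point to loss that remains undiagnosed at day 1. It does not remove the point: for that group the written rule still gives the wrong instruction, and the word that would soften it appears in only one of the two sections and cannot be tested.

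Three stronger readings are tempting, and the documents do not support them:

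- A reader might infer that vision loss from the named hazards would never be counted. Diagnosed causes and Appendix A complications remain reportable.
- A reader might infer that the exemption tilts the main result towards the new device. The complication rate rests on the Appendix A list, where acuity loss is not an item, and no test of an overall adverse-event rate against a comparator is planned.
- A reader might infer that these are new hazards of this device. Sections 5.1 and 5.3 describe vitrectomy in general, and Section 5.2 says the light source is unchanged from the current machine.

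It can also be said that no objective makes acuity an outcome. That is true. The table proposed below is a descriptive safety display, not a new endpoint.

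**Conclusion.** The point holds in a limited form. Section 18.2 removes decreased acuity from adverse-event status without a limit, differs from Section 11.4.1, and overrides the fallback in Section 18.3 for undiagnosed signs. Vision loss with no diagnosis by day 1 may therefore go uncounted as an AE or SAE.

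The effect falls on the secondary day-1 (S)AE objective and can only lower that count. The number of patients cannot be estimated from the documents.

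The conclusion rests on two readings: that a specific exemption prevails over the general recording rule, and that the primary complication rate means the Appendix A events, as Section 6 indicates. If complications were meant to include day-1 signs, the reach would be wider, but nothing in Sections 13.1 or 14.5 says so.

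The change is worth making before data lock. It is more than tidying, because following the rule as written loses safety information.

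**What to change.** - Reconcile Sections 11.4.1, 18.1.2, 18.2 and 18.3 so that they give one status to decreased acuity. The exemption should not extend to loss outside the expected routine course, nor to loss that meets a seriousness criterion. State expressly that the rule for undiagnosed signs applies to such loss. Any clinical bound is for the investigators to set.
- Add to Section 14.5 a descriptive table of acuity change from the pre-operative visit to day 1, by procedure and by tamponade type. Report it whatever the adverse-event coding, with no hypothesis test.

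**Cost.** Wording in the safety sections, a few more AE forms and one table. No new visit or examination is needed, since acuity is already measured at both visits and tamponade is already recorded (Section 11.1). Day-1 acuity should be read with caution in eyes filled with gas or oil, which is the reason for the split by tamponade.
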